## **Outcome Measures**

We will collect the following data during this study.

At eligibility, medical records will be used to provide demographics and baseline information regarding the participant's cerebral palsy, its effects, comorbidities, impairments, and medications taken that might affect the results of this study.

Additionally, we will administer an End of Treatment Questionnaire (15 min) and collect usage and performance logs from the computer and stimulator device in an effort to determine the feasibility of cerebral palsy children using the treatment at home.

At enrollment, we will categorize the participant's general ability to handle objects in daily life using the Manual Ability Classification System (5 min). Using a flowchart, we ask the caregiver to identify which of five levels best describe the child's ability to handle age-appropriate objects. For example, level 1 is "Handles objects easily and successfully", level 2 is "Handles most objects but with somewhat reduced quality and/or speed of achievement", level 3 is "Handles objects with difficulty, needs help to prepare and/or modify activities", level 4 is "Handles a limited selection of easily manage objects in adapted situations, requires continuous support", and level 5 is "Does not handle objects and has severely limited ability to perform even simple actions. Requires total assistance."

At the end of each video game practice session (in lab and at home), we will assess game difficulty and engagement via self-report. A screen will appear at the end of each video game session (180 sessions) that asks the child to rate the difficulty and how engaged they were in the preceding session. The screen will show two visual analog scales (one for difficulty and another for engagement) for the child to report using the computer's touch screen.[6], [7] For difficulty, the choices are: very easy (face with a wide smile), easy (face with a narrow smile), neither easy or hard (neutral face), hard (face with a narrow frown), and very hard (face with a wide frown). For engagement, the choices are: very fun (face with a wide smile), fun (face with a

narrow smile), neither fun or fun or boring (neutral face), boring (face with a narrow frown), and very boring (face with a wide frown). The de-identified data will be saved to the USB drive along with game usage and performance data. This takes 30 seconds during a treatment session.

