## **Potential Risks**

### **Device Risks**

These risks are described as common (which means it might happen greater than 10% of the time), uncommon (which means it might happen about 2-10% of the time), or rare (which means it might happen about less than 1% of the time).

*Fatigue or Pain (Common):* There is a possibility that the concentration and repetition associated with activities during lab sessions may cause "mental fatigue" from the intensity of concentration required during these tasks, or physical fatigue or pain (joint soreness, muscle

ache, or shoulder pain) due to the repetitive tasks. This will vary from person to person. This is similar to what might be experienced after working hard in a traditional occupational therapy session. If the participant experiences such pain or discomfort, we will stop treatments until the pain subsides and adjust the intensity of the treatments to prevent recurring discomfort.

*Motion Sickness (Common):* There is a possibility that the video games can cause motion sickness. Some of the video games feature objects that rotate or move in a way that may cause temporary dizziness or light headedness. We minimized the possibility for motion sickness by making the video animations smooth and by closely matching participant's hand movements with what they control in the video game. We have also designed several games, some of which feature less video movement and lower risk for causing motion sickness. However, if the participant experiences these sensations while playing a video game, we instruct them to stop playing and close their eyes or look away from the video screen. The nausea may go away with rest. If the nausea does not go away after resting or returns after playing the game again, we instruct them to discontinue playing and notify research staff. If a particular game is causing the motion sickness, we will avoid prescribing it to the participant and have them use only the games that do not cause them motion sickness.

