*Uncomfortable Sensation (Common):* Electrical stimulation of a muscle may be perceived as a twitching or vibrating sensation, and may be uncomfortable. Electrical stimulation of a nerve may be perceived as a strong but short shock, and may be uncomfortable. Electrical stimulation of the skin may be perceived as a "pins and needles" sensation and may be uncomfortable. Discomfort associated with electrical stimulation is common, occurring in approximately 40% of subjects if the stimulus parameters are not well-adjusted. Stimulus parameters will be adjusted to your comfort.

*Surface Electrode/Adhesive Skin Irritation (Uncommon):* There is a chance participants may experience a temporary redness of the skin from the electrodes, the conductive gel used with them, or the adhesive used to secure them. Irritation from the electrodes occurs in approximately 10% of subjects. The irritation and redness will go away when the electrodes are removed. Skin irritation from electrical stimulation is rare, but possible. The type of stimulation that will be used minimizes the possibility.

*Electrical Hazards (Rare):* There is a rare possibility of an electrical shock hazard whenever electrical stimulation is used or whenever computers and electrical equipment are used to make measurements. There is a rare possibility of an electrical burn whenever electrical stimulation with surface electrodes is used. Electrical burns will be assessed and treated by the study physician if necessary. Electrical shocks will be assessed and treated by the study physician if necessary, and the equipment will be tested for faults. The equipment to be used has been designed and tested to minimize these risks. Participants will be trained how to use your stimulator safely and will be asked to follow to a list of safety precautions.

*Stimulator Malfunction (Rare):* There is a rare possibility that the stimulator may malfunction and produce painful stimulation even after it has been properly programmed in the laboratory. The sensation may be a sudden burning sensation, which can damage the skin if it does not stop. If participants experience pain from the stimulation, they are instructed to turn off the stimulator, discontinue its use, and contact study personnel.

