### **Data analysis**

We will use a descriptive approach using means and standard errors to assess the effect of hand opening repetitions on the treatment group over time for each outcome. Due to the small sample size in our dataset, we will use a robust estimator to calculate the standard errors.

Upper extremity motor function will be assessed at enrollment, 6 weeks (end of treatment), and at 12 weeks post-treatment by a blinded assessor therapist. All assessments will be performed without any assistance from the stimulator and assessments will take place at least 24 hours after their last treatment session in order to avoid any transient carry-over effect or muscle fatigue. Change scores from the following outcomes will be calculated for each subject.

Descriptive statistics will be used to describe the results across patients and paired t-tests will be used to analyze the pre-post changes.

- Finger movement tracking error (squared sum distance from the target).
- Box and Block Test number of blocks successfully moved.
- Melbourne Assessment 2 percent score (0-100%).
- Assisting Hand Assessment score.

Additionally, adherence will be determined by downloading usage data from both the stimulator and the computer (via a portable USB thumb drive) – which will be used to calculate the percentage of prescribed treatment time completed by each participant. Participants will also be asked at every visit to report any difficulties or complications they may have experienced during home treatment sessions. Then, at the end of treatment, every participant will be interviewed regarding their impression of treatment and dosage, how easy or difficulty it was to use the equipment and play the games, and what changes they would suggest to the equipment or treatment dose, and whether or not they thought the treatment made any difference in their hand function. The number of hand opening repetitions will be recorded at each training session.

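### The planned complications question covers home sessions only, so harms in lab sessions and after treatment are not systematically asked about, recorded or tabulated by arm

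*Combined protocol and SAP*

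**What the plan says.** The Data analysis section, in its paragraph on adherence, states: "Participants will also be asked at every visit to report any difficulties or complications they may have experienced during home treatment sessions". This goes to all participants, so to both arms. No other harms question is scheduled.

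Under Potential Risks, the Device Risks section says of fatigue and pain that the "concentration and repetition associated with activities during lab sessions may cause" them. It labels this risk common, a term it defines as more than 10%. The stated response is "If the participant experiences such pain or discomfort, we will stop treatments until the pain subsides", followed by an adjustment of treatment intensity. No recording step is given.

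Three instructions ask participants to come forward unprompted:
- If nausea from the games persists or returns, they are to "discontinue playing and notify research staff".
- If stimulation is painful, they are to "turn off the stimulator, discontinue its use, and contact study personnel".
- If skin redness lasts or blisters, the stimulator manual described under Risk Mitigation tells them to stop and inform staff.

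Outcome Measures already provides a prompt after every session: "At the end of each video game practice session (in lab and at home), we will assess game difficulty and engagement via self-report". It has no item on pain, nausea or dizziness. The end-of-treatment interview covers impressions, dosage, ease of use, suggested changes and perceived benefit, and does not name harms. The 3-month contact is described only as a blinded motor assessment.

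**The concern.** Read side by side, the two sections do not fit. The plan asks about complications in one setting and places a common risk in the other. Staff who follow the Data analysis section exactly would have no instruction to ask about, or write down, pain or fatigue in a lab session. The same holds for anything that arises or persists in the 12 weeks after treatment.

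Lab sessions also contain a component that the home-session description lacks, namely up to 45 minutes of functional task practice. The wording therefore leaves out a part of the treatment as well as some hours.

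This matters because the pilot is meant to inform a larger trial and has home feasibility in children as a stated purpose. The control arm has the same games and task practice without stimulation, so it is the natural comparator for what stimulation adds in discomfort or harm. Incomplete or uneven collection would weaken that comparison, and no table is planned in which to make it.

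**Working it through.** **Inputs.** From Methods and Procedures: 10 home sessions per week; 2 lab sessions per week for 3 weeks, then 1 per week for 3 weeks; 58 hours in total, the same in both arms. From the paragraph on rehabilitation clinic sessions: up to 90 minutes each. From the Brief Summary: 20 participants. The allocation ratio is not stated, so 10 per arm is an assumption.

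**Step 1: sessions.** Lab: 2 × 3 + 1 × 3 = 9. Home: 10 × 6 = 60.

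**Step 2: the plan's 58 hours.** Lab time is at most 9 × 1.5 = 13.5 h. The remainder is 58 − 13.5 = 44.5 h, or 44.5 × 60 / 60 = 44.5 minutes per home session. With 45 minutes per home session (assumed; the plan gives only a daily ceiling of 90 minutes) the total is 13.5 + 60 × 0.75 = 58.5 h, which agrees with 58 to within half an hour.

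**Step 3: share outside the question.** 13.5 / 58 = 23%, leaving 44.5 / 58 = 77% inside it. The 23% is a ceiling, because lab sessions are specified as up to a given number and length. By session count the share is 9 / 69 = 13%. Outcome Measures mentions 180 video game sessions, which does not match 69, so I rely on hours.

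**Step 4: risks against collection routes.**

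| Risk | Label | Setting named | Unprompted report requested | Arm |
|---|---|---|---|---|
| Fatigue or pain | common | lab sessions | no (treatment is paused) | both |
| Motion sickness | common | none | yes | both |
| Stimulation discomfort | common | none | no | CCFES |
| Skin irritation | uncommon | none | yes | CCFES |
| Electrical shock or burn | rare | none | no | mainly CCFES |
| Painful stimulation from malfunction | rare | none | yes | CCFES |

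Only fatigue or pain is tied to the lab. Of the three unprompted routes, two operate in the CCFES arm alone.

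**Step 5: what fuller collection could show.** The chance of at least one affected child among 10 is 1 − (1 − p)^10. At p = 0.10 it is 65%, and at p = 0.40 it is 99%. The 40% is the protocol's figure for discomfort when stimulation is poorly adjusted. Common harms would usually appear if asked about.

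Comparison is another matter. For 40% against an illustrative 10%, power with 10 per arm is about 33% (normal approximation, two-sided 5%). An observed 4/10 against 1/10 gives a 95% interval for the difference of about −8 to +60 percentage points.

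**The case against.** The strongest reply is that home is the unobserved setting, so it is sensible to ask about it. In the lab a therapist is present, and the protocol has staff pause and adjust treatment when pain occurs. This stands as far as it goes. A reader might infer that lab harms are missed, and the documents do not support that. What they lack is any statement that such events are solicited or recorded.

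A reader might also infer that tolerability cannot be compared between arms. That is too strong. Both arms get the same home question, and it covers about 77% or more of treatment hours. Usage logs from the computer and stimulator supply an exposure denominator. A descriptive home-session comparison is possible, although none is planned. The missing table is a separate omission from the home-only wording.

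Nor are the common harms in general left out. Motion sickness and stimulation discomfort are tied to no setting, so the home question can reach them. It can also reach pain or fatigue from games played at home.

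The post-treatment gap should not be oversold either. No listed risk is described as starting after treatment, skin irritation is expected to clear once electrodes come off, and loss of hand function would show in the blinded 3-month assessments. The position of the sentence, just before the end-of-treatment interview, suggests that it was written with treatment visits in mind. If so, nothing is asked at 3 months. If not, a question about home sessions does not fit the preceding 12 weeks.

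Finally, questions about stimulation or skin at 3 months could unblind the assessor. That is a valid constraint on the fix.

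**Conclusion.** The point holds as a gap in collection and reporting. The only scheduled complications question omits lab sessions, to which the protocol itself assigns a common risk. These make up 9 sessions and up to 13.5 of 58 hours, about 23% of treatment time. Harms after treatment are not systematically asked about either, no record of lab events is specified, and no summary by arm is planned. Because two of the three unprompted routes concern the stimulator, ascertainment may be unequal between arms. The documents do not show by how much.

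The protocol's 40% discomfort and 10% skin-irritation rates do not measure this gap, since neither is tied to lab sessions. Nor does the length of follow-up relative to treatment.

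The 23% rests on the stated schedule, full 90-minute lab sessions and the 58-hour total. The remarks on precision rest on 1:1 allocation. Sample size and efficacy estimates are untouched, but the change is worth making because it is specific and cheap.

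**What to change.** 1. In the Data analysis section, change the scope of the question from home sessions to any time since the last visit, covering lab sessions, home sessions and the period after treatment ends.
2. Ask it in identical words in both arms, at every treatment visit and at the 3-month follow-up. Use existing unblinded staff, or a caregiver form that the blinded assessor does not see.
3. Record the setting and date of each event.
4. Add one descriptive table by arm, giving the number of children and the number of events for each risk named under Device Risks.
5. Optionally, add a pain item and a nausea/dizziness item to the existing end-of-session screen. This would give per-session event counts and reduce reliance on recall, which in weeks 4 to 6 spans about 10 home sessions between weekly visits. It is an improvement rather than a correction.

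Items 1 to 4 cost one reworded sentence, one table and a few minutes at contacts that already take place, plus an arrangement to keep the assessor blinded. Item 5 needs a small edit to the game software. Prompting will raise reported counts, and the table should say so. With about 10 children per arm it should be presented as description, without a test between arms.
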